### **6.1.3.9 Exploratory Safety**

Blood samples collected at visits indicated in the Schedule of Procedures will be stored at the central lab for possible exploratory safety assessments to be determined at a later stage based on the current understanding of toxicology.

### **6.1.4 Treatment Compliance**

Compliance will be monitored using the AiCure daily record of expected and actual medication taken. Any record reflecting that the daily dose was greater than expected will be noted as an overdose event but will be treated as only the expected daily dose (3 capsules) for calculation of compliance in each visit interval.

Compliance over the treatment interval will be calculated as:

Compliance (%) = 100 \* Total number of days kept compliance (took 3 capsules per day)/ number of expected dosing days (The day after V3 to V6/ET visit day).

# [REDACTED]

## Statistical Analysis Plan

Taisho Pharmaceutical R&D Inc.  
Protocol TS121-US201

Final 2.0  
18 Dec 2018  
CONFIDENTIAL

[REDACTED] Statistical Analysis Plan (SAP)

[figure not shown]
Treatment compliance will also be calculated for placebo lead-in, baseline to Week 2, Week 2 to Week 4, and Week 4 to Week 6. Compliance will be calculated for any patient with at least one recorded dose in the interval.

### 6.1.5 Pharmacokinetic Variables and Pharmacogenomic Blood Sampling

A single venous blood sample will be collected for determination of [REDACTED] pharmacokinetics at Visit 6. Analysis of PGx data, if applicable, will be documented in a separate analysis plan.

### 6.1.6 Pharmacodynamic Variables

This study will evaluate blood, urine, saliva and hair samples at specified time points indicated in the Schedule of Procedures, Table 1 for exploratory PD analysis, the results of which may guide in predicting TS-121 response in future trials.

\* : Visit 3 only

\*\* : Visit 3 and 6

# Statistical Analysis Plan

Taisho Pharmaceutical R&D Inc.  
Protocol TS121-US201

Statistical Analysis Plan (SAP)

Final 2.0  
18 Dec 2018  
CONFIDENTIAL

## Figure 2. Pharmacodynamic Schedule

Samples for the following PD markers will be collected at visits indicated in Table 1 and Figure 2:

- Plasma Copeptin
- Salivary Cortisol
- Urine Cortisol
- Hair Cortisol
- Inflammatory Markers (TNF- $\alpha$ , IL-1, IL-6, HS-CRP)

### 6.1.7 Efficacy Variables

Efficacy assessments will be performed at visits indicated in Table 1. The time frame for Montgomery-Asberg Depression Rating Scale (MADRS), Clinical Global Impressions - Severity (CGI-S) and Improvement (CGI-I) Scales, Hamilton Anxiety Scale (HAM-A) and Symptoms of Depression Questionnaire (SDQ) pertains to the previous 7 days. Assessments will be administered by a trained site rater.

Questionnaire interviews will be captured by FDA 21 CFR Part 11 compliant electronic tablets. Results for each question of the HAM-D, MADRS, MGH-ATRQ and SAFER inventory will be captured through this tablet system.

#### ***6.1.7.1 Montgomery-Asberg Depression Rating Scale (MADRS)***

Scoring information for MADRS is defined in Taisho TS121-US201 MADRS Version 1. Primary and secondary efficacy endpoints are based on MADRS total score change from baseline. The MADRS total score is calculated by summing the 10 item scores. The primary endpoint is change in MADRS total score from Visit 3 (Baseline) to Week 6/EOT and the secondary is percentage of MADRS responders, where a responder is defined as  $\geq 50\%$  reduction in total score from Baseline to Week 6/EOT.

# Statistical Analysis Plan

Taisho Pharmaceutical R&D Inc.  
Protocol TS121-US201

Statistical Analysis Plan (SAP)

Final 2.0  
18 Dec 2018  
CONFIDENTIAL

## **6.1.7.2 Clinical Global Impressions - Severity (CGI-S) and Improvement (CGI-I) Scales**

Scoring information for CGI-S and CGI-I is defined in Taisho TS121-US201 CGI-S Version 1 and Taisho TS121-US201 CGI-I Version 1, respectively. The secondary endpoint, percentage of CGI-I improvers, whereby a CGI-I improver is defined as patients with CGI-I score of 1 or 2 (“Very much improved” or “Much improved”).

## **6.1.7.3 Hamilton Anxiety Scale (HAM-A)**

Instructions for HAM-A administration and scoring are provided in HAM-A (SIGH-A, Version 5/92). The HAM-A total score change from Baseline to Week 6/EOT is a secondary endpoint.

## **6.1.7.4 Symptoms of Depression Questionnaire (SDQ)**

Scoring information for SDQ is defined in Taisho TS121-US201 SDQ Version 1. The SDQ total score is calculated by summing the scores of all 44 items. The SDQ total score change from Baseline to Week 6/EOT is a secondary endpoint.

## **6.1.7.5 Handling of Individual Missing Items**

In case  $\geq 25\%$  of items used to calculate a total score for a given scale are missing for one patient and time point then the total scale score for that patient and time point will be considered missing. If  $< 25\%$  of items are missing then the total score will be calculated as the mean of non-missing items multiplied by the total expected number of items and rounded to the nearest integer.

## **6.2 Data Sets Analyzed**

### **6.2.1 Safety Analysis Population**

The safety analysis population will include all patients who received at least one dose of investigational product (including placebo during the placebo lead-in period).

### **6.2.2 Intent to Treat Population**

The Intent to Treat Population will include all patients who were randomized and received at least one dose of randomized treatment.

# Statistical Analysis Plan

Taisho Pharmaceutical R&D Inc.  
Protocol TS121-US201

Statistical Analysis Plan (SAP)

Final 2.0  
18 Dec 2018  
CONFIDENTIAL

## 6.2.3 Exploratory PD Analysis Population

The exploratory PD analysis population will include all randomized patients who completed the baseline assessment of HPA axis and inflammatory biomarkers and have sufficient mental health assessments completed. Missing data will not be imputed and are to be excluded from the analysis.

## 6.2.4 Pharmacokinetic (PK) Analysis Population

The PK analysis population will include all patients who were randomized and received randomized treatment with evaluable PK data and may exclude those that are considered invalid due to relevant missing values, or if any other problems occurring during sampling, laboratory analysis, dosing, or the occurrence of AEs that would invalidate the concentration measurements.

Any data excluded will be described in the clinical study report (CSR).

## 6.3 Statistical Analysis Methods

### 6.3.1 Listings and Descriptive Statistics

All original and derived parameters as well as population characteristics will be listed by subject number and described using summary statistics. Listings will be ordered by treatment group, subject number, date and time. Observations that are spurious (extreme relative to the majority of the data or difference from group median  $>1.5 \times [75^{\text{th}} - 25^{\text{th}}$  percentiles]) will be noted. These will not be altered or removed from any presentation of the data.

Treatment order in summary tables will, in general, be TS-121 10 mg Group, TS-121 50 mg Group and Placebo Group. As appropriate, Total TS-121, Total Placebo Lead-in and Total Screened will also be summarized. Summaries of scheduled events will also be ordered by study period: As grouped in Table 1, screening will include Visit 1 and Visit 1.1 and extend from Day -28 through Day -2, placebo lead-in will include Visit 2 and Visit 2.1 and extend from Day 1 to Day 13 ( $\pm 2$ ), treatment period will include Visit 3 (Baseline), Visit 4, Visit 5 and Visit 6 or EOT and follow-up will include any visit or study day after Week 6/EOT. Frequency counts (number of patients [n]) and percentages will be reported for each qualitative variable. Descriptive statistics (n, arithmetic mean [mean], standard deviation [SD], standard error [SE], minimum,

# Statistical Analysis Plan

Taisho Pharmaceutical R&D Inc.  
Protocol TS121-US201

Statistical Analysis Plan (SAP)

Final 2.0  
18 Dec 2018  
CONFIDENTIAL

median and maximum) will be calculated for each quantitative variable (unless otherwise stated).

All statistical programming will use SDTM data and will be based on SDTM mapping rules for scheduled, unscheduled and repeat visits. No assessment or exclusions other than the mapping specifications will be performed for visits out of the planned visit window.

Listings will include repeat and unscheduled measurements.

The following rules will apply to repeat and unscheduled measurements in summary tables:

- No more than one assessment per patient per time point will be used in the summary of each scheduled safety or efficacy endpoint.
- If the repeated measurement occurs prior to the first dose of study drug for the treatment period, then the last obtained value of any repeated measurement will be used as baseline in the summary tables.
- If the repeated measurement occurs after the first dose of study drug for the treatment period, then the first obtained value of any repeated measurements will be used in the summary tables.

Unless specified otherwise, the baseline used for any change from baseline measurements will be the last measurement prior to the first dose of study drug for the treatment period.

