# Statistical Analysis Plan

Taisho Pharmaceutical R&D Inc.  
Protocol TS121-US201

Statistical Analysis Plan (SAP)

Final 2.0  
18 Dec 2018  
CONFIDENTIAL

laboratory values ordered by test category (biochemistry, hematology and urinalysis), randomized treatment, subject number, laboratory test, date and time will be listed using conventional and SI units [Table 14.3.4.1 and Table 14.3.4.2].

Descriptive statistics (n, mean, SD, SE, CV%, minimum, median and maximum) for non-categorical data including biochemistry, hematology and any quantitative urinalysis will be presented by treatment group and time point for both observed values and changes from baseline in conventional units [Table 14.3.5.1.1] and in SI units [Table 14.3.5.1.2]. Urinalysis categorical results (normal or abnormal) will also be tabulated [Table 14.3.5.2].

Biochemistry, hematology and urinalysis shift tables will be constructed that show the change in quantitative laboratory values (or urinalysis normal/abnormal) from baseline to end of treatment [Table 14.3.5.3.1 through Table 14.3.5.3.3].

Critical ranges for clinically significant laboratory outlier criteria (attached Appendix A) and clinically noteworthy changes (Appendix B) will be used to identify values and trends of potential medical importance. A summary of the number and percentage of patients with clinically significant laboratory outliers, based on Appendix A, for each specified laboratory test will be presented [Table 14.3.5.4.1]. The summary will present across scheduled and unscheduled tests after first dose in Visit 3 and across scheduled and unscheduled test during placebo lead-in period. Clinical laboratory outlier values of individual patients will be presented in a listing [Table 14.3.5.4.2]. Similar analyses will be performed for clinically noteworthy changes from baseline [Table 14.3.5.5.1 and Table 14.3.5.5.2].

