### **6.3.16.4 12-Lead Electrocardiogram**

Electrocardiogram data (ventricular rate, RR, PR, QT, QTcB and QTcF interval data, QRS duration) will be listed [Listing 16.2.9.2.1] with the Investigator interpretation. Any QTcF or QTcB  $>500$  msec will be flagged in the listing. Electrocardiogram data change from baseline will be listed [Listing 16.2.9.2.2] and each flagged to distinguish QTc change from baseline 30 to 60 msec or  $>60$  msec.

Descriptive summaries (n, mean, SD, SE, CV%, minimum, median and maximum) of interval data observed values and change from baseline will be presented by treatment and time point [Table 14.3.6.2.1 and Table 14.3.6.2.2]. Baseline is defined as the scheduled predose assessment of Visit 3. Only if scheduled Visit 3 result is missing, will the latest predose assessment be used as the baseline for that subject number and test.

The categorical analysis of QTcB and QTcF will be presented in a frequency table of patients categorized based on maximum post-baseline QTc ( $\leq 500$  msec or  $>500$  msec) and maximum change from baseline ( $<30$  msec, 30 to 60 msec, and  $>60$  msec) [Table 14.3.6.2.3].

The incidence of abnormalities, based on the clinical interpretations from the Investigator, will be enumerated by treatment group and visit [Table 14.3.6.2.4].

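### Read literally, the SAP's first-value rule keeps a higher same-visit repeat ECG out of the maximum post-baseline QTc table, which can then undercount against the SAP's own ECG listings

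*SAP*

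**What the plan says.** SAP 6.3.1 (Listings and Descriptive Statistics) opens its rules with "The following rules will apply to repeat and unscheduled measurements in summary tables". The first rule is "No more than one assessment per patient per time point will be used in the summary of each scheduled safety or efficacy endpoint". For a measurement repeated after the first dose of the treatment period, "then the first obtained value of any repeated measurements will be used in the summary tables". Listings are treated differently: "Listings will include repeat and unscheduled measurements".

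SAP 6.3.16.4 (12-Lead Electrocardiogram) specifies the categorical output, Table 14.3.6.2.3: "The categorical analysis of QTcB and QTcF will be presented in a frequency table of patients categorized based on maximum post-baseline QTc", with classes of at most 500 and above 500 msec. The same table classifies maximum change as below 30, 30 to 60 or above 60 msec. The section does not say which ECGs feed either maximum. For Listing 16.2.9.2.1, any QTcF or QTcB above 500 "msec will be flagged in the listing". Listing 16.2.9.2.2 flags changes of 30 to 60 and above 60 msec.

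Other worst-value outputs do state their source data. For laboratory outliers, SAP 6.3.16.2 says "The summary will present across scheduled and unscheduled tests after first dose in Visit 3". The hepatotoxicity table in the same section, and the notes to Figures 14.3.1.1 to 14.3.2.2 in SAP Table 3, also bring in unscheduled results.

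**The concern.** A per-patient maximum is meant to capture the worst value on record. A rule that keeps only the first of several readings at a visit can stop it doing so, and an ECG is often repeated because the first one looked borderline or abnormal. The table and the listings would then be built from different data, and the same patient could appear in a lower QTc class in the by-arm table than in the listing behind it.

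Safety is a primary objective, and Protocol 10.5.1.4 asks for the number of patients with QTc above 500 msec by treatment group. Table 14.3.6.2.3 is where a reader will look for that count. Two competent programmers could also produce different counts from the same data: one applying 6.3.1 to every summary table, the other treating the word maximum as an override.

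**Working it through.** The documents give no figure to reproduce, so the check applies the rules to a patient and then asks what can be said about size.

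**1. Does the rule reach the table?** SAP 6.3.1 covers summary tables without exception. SAP Table 2 titles Table 14.3.6.2.3 a categorical summary, and SAP 6.3.16.4 contains no carve-out. On the text, the rule reaches it.

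**2. Same-visit repeat (hypothetical patient).** Baseline QTcF 440 msec; first ECG at Visit 5 is 496; repeat at the same visit is 503; all other readings are lower.

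| Source | Value used | Change | QTc class | Change class |
|---|---|---|---|---|
| Table 14.3.6.2.3 under 6.3.1 | 496 | 496 − 440 = +56 | at most 500 | 30 to 60 |
| Listings 16.2.9.2.1 and 16.2.9.2.2 | 496 and 503 | 503 − 440 = +63 | above 500 | above 60 |

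The table and the listings disagree on both classifications.

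**3. Unscheduled ECG on its own date.** The first-value rule concerns repeated measurements, so it does not apply. The one-value rule limits readings per time point for a scheduled endpoint, and an unscheduled ECG is not a second reading at a scheduled time point. No rule expressly drops it. Equally, nothing says it counts: 6.3.16.4 has no inclusion statement like those for the laboratory outputs, and the SAP 6.3.4 rule that lets an unscheduled value stand in for a missing visit is written for clinical laboratory assessments only. The status is undefined.

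**4. Direction.** A maximum over all readings cannot be lower than one over first readings. The above-500 and above-60 counts under the literal rule can therefore only be equal to or below those from all ECGs.

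**5. Size.** With 60 patients planned per arm, one reclassified patient is 1/60 = 1.7%. How often this happens depends on the repeat rate and on within-visit variability, and the documents give neither. As an illustration only, assume that a visit has two independent normal readings with true QTc μ and within-visit SD s:

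P(first ≤ 500 and repeat > 500) = Φ((500 − μ)/s) × [1 − Φ((500 − μ)/s)]

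| Assumed μ (msec) | s = 5 | s = 10 | s = 15 |
|---|---|---|---|
| 485 | 0.1% | 6.2% | 13.3% |
| 490 | 2.2% | 13.3% | 18.9% |
| 495 | 13.3% | 21.3% | 23.3% |
| 500 | 25% | 25% | 25% |

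These are chances per repeated pair in a patient already close to 500 msec. They are not rates for an arm. An undercount also requires that the repeat was taken and that no other first reading in that patient exceeded 500.

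**The case against.** The strongest reply is that "categorized based on maximum post-baseline QTc" is a specific instruction that overrides a general rule. SAP 6.3.16.4 presents interval summaries by time point and investigator interpretations by visit, but attaches no time point to the categorical table, so a one-value-per-time-point rule fits the first two better. That reading is reasonable. The SAP does not state it, however, and its practice of writing the inclusion out for laboratory outliers and hepatotoxicity points the other way. The ambiguity stands even if the override was intended.

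The table shells and the SDTM mapping rules, which SAP 6.3.1 relies on for scheduled, unscheduled and repeat visits, are outside the documents reviewed here and could settle the point.

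Opportunities for a miss may also be few. The protocol sets out no post-baseline ECG repeat procedure: exclusion criterion 18 allows one confirmatory repeat for eligibility, and the discretion to repeat in Protocol 9.2.7.8 covers laboratory tests.

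The consequence is bounded. The listings keep and flag the values, and under SAP 6.1.3.4 any clinically significant abnormal ECG is reported as an adverse event. Those events are summarised by arm when treatment emergent.

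Finally, Protocol 4.4.3 describes ventricular arrhythmias in Phase 1, not QT prolongation. They are a reason to present cardiac safety carefully, but they are not evidence that QTc values will be high. All of these limits stand, and they reduce the weight of the point without removing it.

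**Conclusion.** The point holds for same-visit repeats. Applied as written, SAP 6.3.1 keeps a higher repeat ECG out of the maximum in Table 14.3.6.2.3, and the by-arm counts above 500 or above 60 msec can fall short of what the listings show. This rests on reading 6.3.1 literally, with no override supplied by the shells or mapping rules.

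Three stronger conclusions that a reader might infer are not supported:

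- **That every unscheduled ECG is dropped.** No rule says so; the SAP leaves its status open.
- **That a sizeable share of large prolongations would be missed.** Any such percentage needs an assumed repeat trigger, ECG variability and true QTc shift, none of which is in the documents. The undercount is probably small.
- **That safety information is lost from the report.** The values stay in the listings; the defect is confined to one summary table.

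This is a minor to moderate correction.

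**What to change.** Add to SAP 6.3.16.4: *Maximum post-baseline QTc and maximum change from baseline are taken over all scheduled, repeat and unscheduled post-baseline ECGs; the one-value-per-time-point and first-value rules in 6.3.1 apply only to by-visit summaries.* Check that the shell for Table 14.3.6.2.3 agrees.

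The cost is one sentence and no new data, and it brings ECG into line with the SAP's handling of laboratory outliers. The above-500 and above-60 counts can only stay the same or rise, probably slightly; the 30 to 60 count may move either way as patients change class. The downside is that some of the rise may be measurement noise, or may come from patients who have extra ECGs because they are monitored more closely, since more readings give more chances of a high maximum. The by-visit summaries are unchanged.

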## 6.3.2 Statistical Significance Level

Any statistical test or confidence interval (CI) will be two-sided and will be performed at the 5% level of significance, unless otherwise stated. No adjustment for multiple comparisons will be performed for calculation of CI or statistical significance.

## 6.3.3 Software

All statistical analyses will be performed using SAS® Version 9.3 and Enterprise Guide Version 7.15 or using SAS Version 9.4

## 6.3.4 Missing Data

Rules for incomplete AE start and end dates/times are described in Section 6.1.3.1. Rules for handling missing efficacy items in calculating total scores are described in Section 6.1.7.5. No imputation of missing data will be performed for safety data or for the exploratory PD analysis.

# Statistical Analysis Plan

Taisho Pharmaceutical R&D Inc.  
Protocol TS121-US201

Statistical Analysis Plan (SAP)

Final 2.0  
18 Dec 2018  
CONFIDENTIAL

In case an unscheduled clinical laboratory assessment was performed within the visit window for a missing assessment then the unscheduled assessment will be included in the visit summary. In these cases the unscheduled assessment closest to the scheduled time will be used.

Missing data are assumed to be missing at random (MAR).

The primary endpoint for efficacy is Week 6/EOT. Efficacy assessments are not planned to be collected at early termination. The primary analysis will include all available efficacy assessments of the Intent to Treat Population. The primary analysis will use MMRM, in which patients with no post baseline assessment are dropped from the model. A sensitivity analysis will assess the Week 6/EOT of each efficacy endpoint (MADRS total score, CGI, HAM-A total score and SDQ total score) based on a multiple imputation method using all patients with a baseline score, including patients with no post baseline assessment.

## 6.3.5 Interim Analysis

No interim analysis is planned.

## 6.3.6 Blinded Efficacy Review

Preliminary blind review of efficacy will be conducted prior to database lock.

## 6.3.7 Randomization Schema and Codes

Subject number, randomization date and treatment will be listed [Listing 16.1.7].

## 6.3.8 Documentation of Statistical Methods

In addition to this SAP, the record of statistical model calculations will be included in Section 16.1.9 of the CSR.

## 6.3.9 Patient Disposition

A record of IRT data, including subject number, placebo lead-in date, randomization date, treatment, first and last dose dates, screen/placebo lead-in fail date and primary reason, the completion status, the date of discontinuation and the reason for discontinuation of all screened patients will be listed. Unblinding date and reason will be listed if any unblinding event occurs [Listing 16.2.1.1]. The number of patients randomized, received the randomized treatment and the frequency and percentage of patients completing the study, patients withdrawing early, and primary reason for withdrawal will be summarized by treatment and overall for all randomized

# Statistical Analysis Plan

Taisho Pharmaceutical R&D Inc.  
Protocol TS121-US201

Statistical Analysis Plan (SAP)

Final 2.0  
18 Dec 2018  
CONFIDENTIAL

patients [Table 14.1.1.1]. The number of patients entered placebo lead-in period and randomized or failed will be summarized by treatment and overall [Table 14.1.1.2]. An overall summary table of patients who signed informed consent with numbers of patients who screen failed prior to or after entering placebo lead-in, and reasons for failures will also be presented [Table 14.1.1.3].

Disposition information will be presented in a flow diagram of number of patients screened, screen failures before start of placebo lead-in (Visit 2), placebo lead-in screen failures, patients randomized, patients dosed, reasons for any patient randomized but not dosed, total number of patients receiving double-blind treatment, number per treatment group starting double-blind treatment, number per treatment group of patients completing the study and summary counts, by treatment group, of the reasons that patients discontinued from the study [Figure 14.1.1].

